11.2 Assessment and Reporting of a Serious Adverse Event (SAE)

An SAE may be due to the participant's underlying critical illness, or may be directly related to enrolment in the study (i.e. it is unlikely to have occurred if the patient were not enrolled in the study).

It is the responsibility of the site PI to ensure all SAE's are assessed to determine causality, that is, to determine the likelihood that the SAE was caused by a study intervention.

The site PI should ask the attending physician caring for the patient at the time the SAE occurred to assist with assessment of causality. An SAE may be assessed as being unrelated, unlikely related, possibly related, probably related, or definitely related to the study intervention, according to the definitions provided below. In cases where causality is "unknown" or the site PI and attending physician have disagreement or doubt regarding whether an SAE has "unlikely" relation vs. "possible" relation to the study intervention, the site PI must contact one of the study co-PIs/sponsors ([name] or [name]) to discuss and adjudicate the SAE.

Causality	
Unrelated	A definitive alternative etiology for the AE must exist
Unlikely	Must have 2: 
 • No temporal relationship to the intervention • Could readily have been produced by the patient's clinical state or have been due to environmental or other interventions • Does not follow a known pattern of response to intervention • Does not reappear or worsen upon intervention re-exposure
Possible	Must have 2: 
 • Reasonable temporal relationship to the intervention

	
 • Could not have readily been produced by the patient’s clinical state or have been due to environmental or other interventions • Follows a known pattern of response to intervention • Disappears or decreases with replacement of intervention with standard of care procedures and recurs with re-exposure
Probable	
Must have 3:
 
 • Reasonable temporal relationship to the intervention • Could not have readily been produced by the patient’s clinical state or have been due to environmental or other interventions • Follows a known pattern of response to intervention • Disappears or decreases with replacement of intervention with standard of care procedures and recurs with re-exposure
Definite	
Must have all 4:
 
 • Reasonable temporal relationship to the intervention • Could not have readily been produced by the patient’s clinical state or have been due to environmental or other interventions • Follows a known pattern of response to intervention • Disappears or decreases with replacement of intervention with standard of care procedures and recurs with re-exposure

It is the responsibility of the site investigator to identify and report SAEs occurring between patient enrolment and study completion (enrolment occurs once patient or SDM has provided consent and study completion occurs once patient achieves successful extubation, successful ICU discharge, hospital discharge, dies, or day 90 post randomization, whichever comes first).

SAEs are to be documented in source and in the Serious Adverse Events eCRF. Whenever possible, if a unifying diagnosis can be made, all associated complications should be grouped together and reported as one SAE. If the patient expires the site investigator is required to complete a SAE assessment in their source documents. Sites can refer to the Data Entry Guidelines for instructions on how to access the eCRF. The eCRF system (Medidata RAVE) will notify the study PI, CC and Medical Monitor of the SAE so that it may be immediately assessed for further action in any applicable local or federal requirements.

The investigator or his/her designate will promptly report SAEs with probable or definite relation to study intervention within 24 hours of becoming aware of the event, and update as additional information becomes known. Each site will also need to report SAEs with probable or definite relation to a study intervention to the local REB according to local institutional requirements.

The site may be asked for additional information to assist with the assessment, and a narrative with appropriate clinical context should be included in each SAE reported.

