B11	Plan to extubate/discontinue mechanical ventilation within < 24 hours (Reassess within 24 hours)
B12	Patient currently on ECMO (Reassess patient once off ECMO)
C9.	Plan for surgery or complex procedure that will require full ventilation to be done prior to attempting extubation (e.g. Procedure requiring neuromuscular blockade and/or heavy sedation, such that patient would be apneic, or not be able to trigger ventilator) (Reassess after surgery/procedure complete)

B. Enrolment Exclusion Criteria:

B7	Extubated
B8	Died
B9	Patient has met enrolment inclusion criteria B1-B5 AND has tolerated pressure support of 0-20 cm H ₂ O or proportional assist ventilation of 0-85% for ≥ 24 consecutive hours (including time on CPAP, t-piece, or tracheostomy mask). (Note (1):that it is acceptable to include a patient who has been tried on pressure support or proportional assist ventilation but has required pressures > 20 cmH ₂ O or assistance $> 85\%$ or has required return to A/C ventilation within the 24 hour time window; Note (2): B9 does not apply to patients on ECMO.)
B10	Patient transferred to a non-participating centre

For patients meeting all A. Screening and B. Enrolment Criteria, the treating ICU physician will be asked to provide verbal consent to (i) enroll the patient, (ii) proceed with standardized tests to determine eligibility for randomization, (iii) randomize the patient if eligibility criteria are met, and (iv) enable the research team to approach the patient/SDM for consent. The standardized tests are part of routine clinical care and include a trial of pressure support and screening for a trial of spontaneous breathing. **If the ICU physician plans to extubate the patient within 24 hours, enrolment may be deferred** until the next calendar day and the patient reassessed to determine if the patient has passed an SBT or is extubated. If the patient is not extubated by the following morning and/or fails an SBT, the patient should then be enrolled and proceed to randomization criteria. Patients on ECMO are not eligible for enrolment until off ECMO.

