Eligible patients or their substitute decision makers (SDMs) will be approached for consent to participate in the clinical trial as soon as possible after the treating physician has provided verbal consent. The patient/SDM **will be provided a Letter of Information and asked to provide written informed consent** to proceed with (i) randomization if eligibility criteria are met during standardized tests and (ii) use of data collected from time of enrolment through to study termination. Obtaining informed consent prior to randomization is preferred; however, randomization of eligible patients may proceed with deferred consent if the patient is incapable and no SDM can be contacted despite at least two documented attempts. (See section 14.3 for further information on obtaining informed consent).

Physicians may institute pressure support at any time according to clinical discretion and usual care. The pressure support trial is intended for cases where the patient has not yet been placed on pressure support ≤ 20 cm H₂O (above PEEP) by the treating physician. The Pressure Support Trial (PST) is the first test in a series of

tests to determine if a patient is ready for randomization. Prior to initiating the PST, the treating physician must approve proceeding with the standardized tests and randomization if eligible.

C. Pressure Support Trial Inclusion Criteria:

C2.	Upon review of Screening and Enrolment criteria (A and B), the patient still passes.
C3.	Treating physician has provided verbal consent to proceed with standardized tests and randomization if eligibility criteria are met

C. Pressure Support Trial Deferral Criteria

C6.	High dose vasopressor requirements (i.e. epinephrine or norepinephrine >0.5 µg/kg/min or equivalent) OR patient requiring an increase in dose of vasopressor within 6 hrs
C7.	Active cardiac ischemia (dynamic ST changes on monitor or ECG within 6 hours)
C8.	Unstable arrhythmias (HR>140 or <50) with clinical signs of low cardiac output or or SBP<80 mmHg
C10.	Receiving a "strict lung protective" ventilation strategy for ARDS (eg. Order on chart to keep Vt ≤6 mL/kg PBW)

C. Pressure Support Trial Exclusion Criteria

C12.	Treating physician has declined consent
------	---

Patients already on pressure support of ≤20 cm H₂O (above PEEP) for >30 minutes will be considered to have passed the Pressure Support Trial and will move on to the next stage of enrolment.

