1. Disconnect endotracheal tube from ventilator circuit and place patients on T-piece* with FiO₂ 0.40. (For patients with tracheostomy, place patients on tracheostomy mask trial with FiO₂ 0.40)
2. Monitor patient for 30-120 minutes:
3. FAIL/ SBT Termination: Terminate the SBT and return patient to prior ventilator settings if at any time one of the following occur:
 - a. Respiratory Distress
 - b. Clinical Instability
 - c. Increased somnolence with elevated pCO₂ and/or pH<7.32
 - d. Desaturation with SpO₂ <90% on FiO₂ 0.40

**for the purposes of this study, the Sponsor considers SBT performed with patients connected to ventilator on flow-by with CPAP of 0 cmH₂O and FiO₂ 0.40 to be equivalent to SBT performed on T-piece with FiO₂ 0.40.*

Following the SBT, proceed to the final stage (E).

In the final stage (E), patients will be considered eligible for randomization if the following criteria are met.

E. Randomization Inclusion Criteria

C1.	Patient/SDM has provided consent OR Plan to obtain deferred consent as Patient incapable and no SDM available to provide consent within the randomization window
E1.	Upon review of Criteria A, B, and C, the patient still passes and the patient has passed the PST.
E2.	Does not meet Weaning Criteria OR Fails the ZERO CPAP Trial OR Fails the SBT

E. Randomization Exclusion Criteria:

B9	Patient has met enrolment inclusion criteria B1-B5 AND has tolerated pressure support of 0-20 cm H ₂ O or proportional assist ventilation of 0-85% ≥24 consecutive hours (including time on CPAP, t-piece, or tracheostomy mask). Note (1): It is acceptable to include a patient who has been tried on pressure support or proportional assist ventilation but has required pressures >20 cmH ₂ O or assistance >85% or has required return to A/C ventilation within the 24 hour time window; Note (2): B9 does not apply to patients while on ECMO
C4.	Patient/SDM has declined consent
C5.	Patient incapable and no SDM available to provide consent (not applicable if plan to obtain deferred consent)

E3.	Passed SBT on t-piece, FiO ₂ 0.40 for 30-120 minutes
E4.	Approval withdrawn (by physician or patient/SDM)

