10.5 Administration of Intervention

Switching ventilator mode to PSV or PAV+ with adjustment of the settings according to the assigned PSV or PAV+ Ventilation Strategy will indicate administering the intervention. The intervention (the PSV or PAV+ Ventilation Strategy) is administered continuously from time of randomization until study completion (study completion occurs at time of successful extubation/successful termination of invasive MV, successful ICU discharge, hospital discharge, death or 90 days post randomization, whichever comes first).

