14.3 Informed Consent

It is an obligation of the participating site to administer informed consent with the participant or Substitute Decision Maker (SDM) by means of a dated and signed informed consent form. Consent should be obtained prior to randomization whenever possible; however, if the participant is incapable of providing informed consent and no SDM is available within the randomization window, consent must be sought as soon as possible after randomization (provided that the local Research Ethics Board has provided approval for deferred consent). The informed consent form must be written in the local language in accordance with local laws and regulations.

‘Informed consent’ also implies individual discussion with the participant/SDM about the nature of study treatment and examinations to be conducted in a language that is easy to comprehend. The participant/SDM should fully understand that his/her refusal to participate in the study will not affect the quality of medical care. In addition, the participant/SDM must be informed that, without disclosing his/her name, relevant medical data will be disclosed to the Coordinating Centre (CC), that his/her medical records will be inspected during on-site monitoring, and may be inspected again by auditors and/or regulatory authorities.

The participant/SDM should be informed in writing that his/her medical data relevant to this study will be stored and analyzed while maintaining confidentiality in accordance with local data protection laws. All data transferred to the eCRF and any process derived from the eCRF will be de-identified. In cases where the participant dies prior to being capable of providing informed consent, and there is no SDM available, the de-identified data will be included in the eCRF in centres where the Research Ethics Board permits waived consent under such circumstances.

Should a protocol amendment be made, the informed consent form may be revised to reflect the changes in the protocol. It is the responsibility of the investigator to ensure that an amended informed consent form is reviewed and approved by the local REB, and that it is signed by all participants/SDMs subsequently entered in the study and those currently in the study, if affected by the amendment.

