4.6.3 Safety Sample

Safety analysis will include all randomized patients.

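### Protocol 11.2 opens the SAE reporting window at patient or SDM consent, so under deferred consent the time from randomization to consent is treated but lies outside it

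*Protocol*

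**What the plan says.** Protocol 11.2 sets the duty: "It is the responsibility of the site investigator to identify and report SAEs occurring between patient enrolment and study completion". A parenthesis in the same sentence fixes both ends of the window: "enrolment occurs once patient or SDM has provided consent and study completion occurs once patient achieves successful extubation", with successful ICU discharge, hospital discharge, death and day 90 as alternative ends.

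Randomization can come before that consent. Protocol 7.3 says that "randomization of eligible patients may proceed with deferred consent if the patient is incapable and no SDM can be contacted" after at least two documented attempts. Randomization criterion C1 is met by a "Plan to obtain deferred consent as Patient incapable and no SDM available to provide consent within the randomization window". Section 14.3 adds that in such cases "consent must be sought as soon as possible after randomization", provided the local REB has approved deferral. It sets no upper limit on the delay. It also foresees death before consent with no SDM available, and keeps the de-identified data where the REB permits waived consent.

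Exposure starts at randomization: under 10.5 the assigned strategy "is administered continuously from time of randomization until study completion".

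Protocol 7.3 uses enrolment for an earlier moment. Before the patient or SDM is approached, "the treating ICU physician will be asked to provide verbal consent to (i) enroll the patient".

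On the analysis side, SAP 4.6.3 states: "Safety analysis will include all randomized patients". Protocol 6.4 also starts from randomized participants, with a condition on having received PAV+ or PSV. Neither population depends on consent.

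**The concern.** A reporting window should cover the whole time a patient is exposed to the assigned strategy. Here it opens at consent while exposure opens at randomization. For patients who consent first this makes no difference. For deferred-consent patients it leaves an interval at the start of treatment in which the protocol gives the site no stated duty to report an SAE in the eCRF.

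Three things depend on those reports. SAE frequency and incidence by arm is a primary safety endpoint (Protocol 6.4). The eCRF entry is what alerts the study PI, the coordinating centre and the Medical Monitor (11.2). The DSMB's review of related SAEs (11.1, 11.4) and of aggregate SAEs (SAP 9.1, 9.2) also starts from what sites report.

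**Working it through.** No figure in the plan is at issue, so the check compares the order of events. Let R be randomization, C patient or SDM consent, and E study completion as listed in 11.2.

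- Exposure to the assigned strategy (10.5): from R to E.
- SAE reporting window (11.2): from C to E.
- Uncovered treated time: from R to the earlier of C and E, if C is later than R; otherwise none.

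| Consent route | Order of events | Treated time outside the window |
|---|---|---|
| Consent before randomization | C, R, E | None |
| Deferred consent, later given | R, C, E | R to C |
| Death before any consent | R, E, with no C before E | All of it (R to E) |

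Next, whether any other passage moves the start of the window:

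1. Protocol 11.1 to 11.4 contain no rule that starts the window at randomization or makes it retroactive once deferred consent is given.
2. The 7.3 use of enrolment, at the physician's verbal agreement, would close the gap. But 11.2 carries its own explicit definition, and that is the one a site completing an SAE form would read.
3. SAP 9.2 has coordinators review records over the time a patient takes part in the trial, without saying when that begins.
4. Protocol 10.2 puts consent before any study procedure. If that governed there would be no gap, but it contradicts the deferral allowed in 7.3, 14.3 and Appendix A.

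Then, what is still captured inside the gap:

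- Deaths: 11.1 and 11.2 require an SAE assessment in source documents for any patient who dies, with no consent condition, and mortality is a separate safety endpoint (6.4).
- Device incidents: 11.3 requires reporting within 24 hours and is not tied to enrolment or consent.
- Non-fatal SAEs that are not device incidents: nothing equivalent.
- eCRF reporting of fatal SAEs: still bounded by the window, because an assessment held in source documents is not an eCRF report.

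On size, the uncovered treated time is the sum, over deferred-consent patients, of the interval from R to the earlier of C and E. That needs the share randomized under deferred consent and the distribution of the delay. The documents give neither.

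**The case against.** The best case on the other side is that this is a conflict of terms and not a plan to leave treated patients unwatched. Consent under 7.3 covers data from enrolment onward, and in that section enrolment precedes the approach to the patient or SDM. The flow diagram in SAP 4.3 also treats patients who declined after deferred consent as enrolled. Section 11.2 asks for causality assessment of all SAEs. Where the REB waives consent after a death, 14.3 puts the de-identified data in the eCRF, and the SAE form is part of the eCRF. Deferral is meant to be the exception, and sites may well report from randomization in practice. All of this stands. It bears on intent and likely conduct, but it does not change the explicit start point in 11.2.

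Several stronger readings are tempting, and the documents do not support them:

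- *Deaths before consent go unseen.* They do not, given the source-document assessment and the mortality endpoint.
- *SAE rates will be understated and the DSMB will not see these events.* That holds only if sites apply 11.2 literally. The DSMB also reviews safety reports twice a year and may ask for further analyses (11.4). The supportable statement is that it is not assured of seeing these events.
- *The gap covers the most dangerous period.* No passage says so. Protocol 11.1 anticipates no added risk, and 4.4.2 reports no intervention-related adverse events in the pilot trial.
- *The comparison between arms is biased.* The consent route is settled before randomization through C1, so the share deferred should balance across arms, and SAP 9.3 plans only a descriptive SAE analysis. Differential reporting is possible in an open-label trial but is not shown.

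**Conclusion.** The point holds as a defect in the wording of the reporting rule. As written, 11.2 excludes from the eCRF reporting duty any SAE between randomization and deferred consent, and the window never opens for a patient who dies before consent. The events left without protection are mainly non-fatal SAEs, together with the eCRF reporting of fatal ones. Because both safety populations rest on randomization, such events can be missing from the numerator while the patients remain in the denominator.

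The size is unknown. A reader might try to estimate it from the blinded median of 6.8 days in Protocol 12.1. Under exponential times, the share of patient-time in the first d days is 1 − exp(−d·ln 2/6.8), which is 9.7%, 18.4% and 26.3% for d = 1, 2 and 3. With an assumed 20% to 50% deferred and a 2-day delay, that gives 3.7% to 9.2% of all on-study time. These figures should not be relied on. The deferral rate and the delay are invented, and 6.8 days is the median time to successful liberation, whereas the 11.2 window also ends at death or discharge. The conclusion does not need them. It rests only on the definition in 11.2 being applied as written and on some patients being randomized under deferred consent.

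**What to change.** - In Protocol 11.2, open the SAE window for every randomized patient at the earlier of patient or SDM consent and randomization.
- State there that SAEs before deferred consent, including those in patients who die before consent, are reported in the eCRF within the limits of the local REB's deferred or waived consent approval.
- Give enrolment one meaning in 7.3 and 11.2, define the start of the participation period in SAP 9.2 to match, and reconcile the 10.2 statement on consent with deferral.

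The cost is a few more SAE forms and a wording amendment, which under Protocol 10.7 needs REB approval before it takes effect. No treatment or analysis method changes.

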11.3 Definition and Reporting of an Adverse Device Effect

Subject to section 59 of the Medical Device Regulations, any incident that comes to the attention of the investigator which meets the following conditions must be reported to the coordinating centre within 24 hours of becoming aware of the incident:

(1) Incident is related to a failure of the device or deterioration in its effectiveness, or any inadequacy in its labeling or in its directions for use;

AND

(2) Has led to the death or a serious deterioration in the state of health of a patient, user or other person, or could do so were it to recur.

In such a situation, the investigator must complete the study Incident Report and submit the report to the coordinating centre within 1 business day of becoming aware of the incident. The following information will be required: date of the incident, details of the incident, course of action taken, and other relevant details.

Follow-up reports must be provided to the coordinating centre as any new information becomes available. The device manufacturer will report these incidents to the Medical Devices Bureau of Health Canada within the timelines specified in section 60 of the regulations.

(<http://laws-lois.justice.gc.ca/eng/regulations/sor-98-282/page-13.html#h-42>)

11.4 Data Safety Monitoring Board (DSMB)

The DSMB will review safety reports biannually. The DSMB will have the ability to request additional safety analyses and make recommendations about the safe conduct of the trial. The DSMB Chair will review all serious adverse events classified as probably or definitely related to enrolment in the trial within 7 days and communicate directly with the co-principal investigators, who in turn will communicate back to the Steering Committee.

